12.3. Appendix 3: Data Display Standards & Handling Conventions

12.3.1. Reporting Process

Software

 The currently supported versions of SAS software will be used.
Analysis Datasets

 Analysis datasets will be created according to CDISC standards (SDTM IG Version 3.2 & ADaM IG Version 1.0) For creation of ADaM datasets (ADCM/ADAE), the same version of dictionary datasets will be implemented for conversion from SI to SDTM.
Generation of RTF Files

 RTF files will be generated for all reporting efforts described in the RAP.

12.3.2. Reporting Standards

General

 The current GSK Integrated Data Standards Library (IDSL) will be applied for reporting, unless otherwise stated (IDSL Standards Location: https://spope.gsk.com/sites/IDSLLibrary/SitePages/Home.aspx): 
 4.03 to 4.23: General Principles 5.01 to 5.08: Principles Related to Data Listings 6.01 to 6.11: Principles Related to Summary Tables 7.01 to 7.13: Principles Related to Graphics Do not include subject level listings in the main body of the GSK Clinical Study Report. All subject level listings should be located in the modular appendices as ICH or non-ICH listings
Formats

 GSK IDSL Statistical Principles (5.03 & 6.06.3) for decimal places (DP's) will be adopted for reporting of data based on the raw data collected, unless otherwise stated. Numeric data will be reported at the precision collected on the eCRF. The reported precision from non eCRF sources will follow the IDSL statistical principles but may be adjusted to a clinically interpretable number of DP's.
Planned and Actual Time

 Reporting for tables, figures and formal statistical analyses: 
 Planned time relative to dosing will be used in figures, summaries, statistical analyses and calculation of any derived parameters, unless otherwise stated. The impact of any major deviation from the planned assessment times and/or scheduled visit days on the analyses and interpretation of the results will be assessed as appropriate. Reporting for Data Listings: 
 Planned and actual time relative to study drug dosing will be shown in listings (Refer to IDSL Statistical Principle 5.05.1). Unscheduled or unplanned readings will be presented within the subject's listings.

Unscheduled Visits	

 Unscheduled visits will not be included in summary tables and/or figures except for determining baseline or determining the worst-case values. All unscheduled visits will be included in listings. 	
Descriptive Summary Statistics	
Continuous Data	Refer to IDSL Statistical Principle 6.06.1
Categorical Data	N, n, frequency, %
Graphical Displays	

 Refer to IDSL Statistical Principals 7.01 to 7.13. 	

12.3.3. Reporting Standards for Pharmacokinetic

Pharmacokinetic Concentration Data	
PC Windows Non-Linear (WNL) File	PC WNL file (xpt format) for the non compartmental analysis will be created according to SOP 314000(2.0). Note: Concentration values will be imputed as per GUI_51487
Descriptive Summary Statistics, Graphical Displays and Listings	Refer to IDSL PK Display Standards. Refer to IDSL Statistical Principle 6.06.1. Note: Concentration values will be imputed as per GUI_51487 for descriptive summary statistics/analysis and summarized graphical displays only.
Pharmacokinetic Parameter Derivation	
PK Parameter to be Derived by Programmer	The following plasma PK parameters will be derived by the Programmer: R ₀ , C _τ The following urine PK parameters will be derived by the Programmer: Ae 12h, Ae(t1-t2), Fe%, CL _r , C _τ
Pharmacokinetic Parameter Data	
Is NQ impacted PK Parameters Rule Being Followed	Yes, refer to [Standards for Handling NQ Impacted PK Parameters].
Descriptive Summary Statistics, Graphical Displays and Listings	Refer to IDSL PK Display Standards.

12.4. Appendix 4: Derived and Transformed Data

[figure not shown]
12.4.1. General

Multiple Measurements at One Analysis Time Point

 • Mean of the measurements will be calculated and used in any derivation of summary statistics but if listed, all data will be presented. • The worst finding/interpretation associated with multiple measurements as the finding/interpretation for that time point. • Participants having both High and Low values for Normal Ranges at any post-baseline visit for safety parameters will be counted in both the High and Low categories of “Any visit post-baseline” row of related summary tables. This will also be applicable to relevant Potential Clinical Importance summary tables.
Study Day

 • Calculated as the number of days from First Dose Date: 
 • Ref Date = Missing → Study Day = Missing • Ref Date < First Dose Date → Study Day = Ref Date – First Dose Date • Ref Date ≥ First Dose Date → Study Day = Ref Date – (First Dose Date) + 1

12.4.2. Study Population

Age

 • GSK standard IDSL algorithms will be used for calculating age where birth date will be imputed as follows: 
 ○ Any subject with a missing day will have this imputed as day ‘15’. ○ Any subject with a missing day and month will have this imputed as ‘30th June’. • Birth date will be presented in listings as ‘YYYY’.
Body Mass Index (BMI)

 • Calculated as Weight (kg) / Height (m)²
Micro-ITT Population

 • Micro-ITT population include participants who receive at least 1 dose of gepotidacin and have a qualifying bacterial uropathogen at Baseline from a quantitative bacteriology culture of a pretreatment clean-catch midstream urine specimen. • The algorithm of the qualifying bacterial uropathogen is presented in Figure 2. If there're 2 uropathogens identified at baseline for a participant, the participant will be included in the micro-ITT population if at least 1 of the 2 uropathogens is ≥10⁵ CFU/mL.

Figure 2 Baseline Algorithm for the Microbiological intent-to-Treat Population

CFU=colony-forming units; micro-ITT=Microbiological Intent-to-Treat.

12.4.3. Safety

Adverse Events
AE'S of Special Interest

 Cardiovascular (CV) events Gastrointestinal events A comprehensive list of Medical Dictionary for Regulatory Activities (MedDRA) terms based on clinical review will be used to identify each type of event.
Adverse Events with Missing Relationship or Missing Serious Indicator

 If the relationship to study treatment is missing for a treatment-emergent AE, it'll be considered as related to the study treatment. If the serious indicator "Was event serious?" is missing, the AE will be considered as SAE. Adverse events with missing relationship or missing serious indicator will be presented as it is in listings, but will be treated as related AEs or SAEs in summary tables.

12.4.4. Efficacy

Microbiology Procedures

- Microbiology data will be received from two sources
 - Central laboratory
 - Excel spreadsheets from the study microbiologist and/or clinical scientist
- The central laboratory will analyse the bacteriology urine samples by conducting a Gram stain, quantifying and identifying uropathogens and will perform susceptibility testing as listed below.
 - Broth microdilution results (MIC) on all gram-positive uropathogens for gepotidacin, ampicillin, trimethoprim-sulfamethoxazole, trimethoprim, sulfisoxazole, ciprofloxacin, levofloxacin, nitrofurantoin and vancomycin.
 - Broth microdilution results (MIC) on all gram-negative uropathogens for gepotidacin, ampicillin, amoxicillin/clavulanic acid, ceftolozatone/tazobactam, ceftazidime/avibactam, piperacillin/tazobactam, ceftazidime/avibactam, cefazolin, ceftriaxone, meropenem, amikacin, gentamicin, trimethoprim-sulfamethoxazole, trimethoprim, sulfisoxazole, ciprofloxacin, levofloxacin, nitrofurantoin and vancomycin
 - Amoxicillin/clavulanic acid is tested in the ratio of 2:1, concentrations for amoxicillin/clavulanic acid will be expressed as the amoxicillin concentration. Piperacillin/tazobactam and ceftolozane/tazobactam are tested with the concentration of tazobactam fixed at 4 mg/L, concentrations for piperacillin/tazobactam and ceftolozane/tazobactam will be expressed as the piperacillin and ceftolozane concentration, respectively. Ceftazidime/avibactam is tested with the concentration of avibactam fixed at 4 mg/L, concentrations for ceftazidime/avibactam will be expressed as the ceftazidime concentration. Trimethoprim-sulfamethoxazole is tested in the ratio 1:19, concentrations for trimethoprim-sulfamethoxazole will be expressed as the trimethoprim concentration.
 - Gradient diffusion results (MIC) on all gram-negative and gram-positive uropathogens for fosfomycin
 - All gram-negative uropathogens will be also be tested by broth microdilution (MIC) to determine indicate production of extended spectrum beta-lactamases (ESBLs). In accordance with the Clinical and Laboratory Standards Institute (CLSI) M100 guidelines (Table3A), ESBL production may be indicated by a MIC result of >1 mcg/mL for ceftazidime, ceftazidime, cefotaxime or aztreonam for *E. coli*, *K. pneumoniae* or *K. oxytoca* or a MIC result of >1 mcg/mL for ceftazidime, cefotaxime or cefpodoxime for *P. mirabilis*.
- The data from the study microbiologist and/or clinical scientist will include clarification of which isolates should be labelled as uropathogens and qualifying uropathogens and a determination of whether the susceptibility results for identically labelled uropathogens from the same participant at the same visit differ enough to classify the uropathogens as separate.

Microbiological Data Procedures

 • Statistics and Programming will identify all cases within the central laboratory dataset where two or more uropathogens of the same genus and species have been identified for the same participant at the same visit. • An excel file containing a list of these uropathogens and the associated quantitative bacterial counts and MIC results for each isolate will be provided to the microbiologist. • The microbiologist will review the list and determine if the isolates are the same or different strains of the identified uropathogen based on the susceptibility data patterns. 
 • If there is a ≥ 4-fold difference in MIC to one member of two or more antibiotic classes, then the two isolates will be considered two different strains and both will be used in the analysis. • Otherwise, only one isolate will be kept for analysis based on a pre-defined algorithm. • The microbiologist will add a flag to the list to indicate which of the duplicate records to keep. All records will be kept in the SDTM datasets, and those records that are deemed to be duplicates will be removed from the final Analysis Data Model (ADaM) dataset. • For participants whom the microbiologist has indicated that both sets of uropathogen records should be maintained, Statistics and Programming will provide all central laboratory data from all visits for the particular uropathogens to the microbiologist. • Should the same uropathogen be presented at additional visits, the microbiologist, with the use of the MIC result, will make a determination as to which of the baseline uropathogens has been isolated at this new visit. • Statistics and Programming will also provide a list of all distinct isolates (by participant, visit, identification, and quantitative bacterial count) from the central laboratory to the microbiologist and clinical scientist. • The microbiologist and clinical scientist will provide an excel spreadsheet containing a list of decoded uropathogen codes and a flag to indicate which items within the code list are uropathogens and qualifying uropathogens for this protocol. This flag will then be merged into the SDTM dataset.
Fold Change

 • Fold change will be used to describe how much the MIC for gepotidacin changes between baseline and subsequent visits for the same bacterial species from the same participant. • Fold change will be calculated (in doubling dilutions) as the ratio of the MIC at the subsequent visit to the MIC at baseline visit.
Susceptibility Interpretations

 • Susceptibility interpretations will be calculated and reported by the central laboratory and will be based on the CLSI M100 guidelines in effect at that time the bacterial isolate is tested. • Since CLSI breakpoints for certain drug/bug combinations can change in new yearly editions of M100 guidelines, as GSK and/or the central laboratory become aware of relevant breakpoint changes, the central laboratory will identify any reports which would qualify as needing a change in interpretation (e.g. a MIC value that was originally reported as susceptible, and would now be considered resistant based on the new breakpoint), and will issue amended reports. • The final clinical database will report interpretations according to the most recent CLSI M100 interpretations regardless of what the breakpoints were at the time the isolate was initially tested.

Quantitative Bacterial Counts

- The central laboratory will quantitatively determine the growth of bacterial uropathogens from culture of participant urine samples.
- The central laboratory will report the following quantification results
 - If there is no growth on the culture plates for a urine sample:
 - No growth ($<10^3$)
 - If there is growth on the urine culture plates for a urine sample, each uropathogen will receive an associated colony count:
 - 10^3 - $<10^4$
 - 10^4 - $<10^5$
 - $>10^5$
- At subsequent visits, determination of 'no growth' for individual uropathogens will need to be derived from an overall urine culture result of no growth (meaning there was no growth on the urine culture plates) or no identification/quantification being reported for that specific uropathogen (assuming that a urine sample was taken and that results were reported).
- If the bacterial sample at a subsequent visit is not collected then it's considered as "unable to determine" for the uropathogens identified at baseline.

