7.4. Blinding

This will be an open-label study.

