4. ANALYSIS POPULATIONS

Population	Definition / Criteria	Analyses Evaluated
Safety	
 All participants who take at least 1 dose of gepotidacin. 	
 Study Population Safety
PK	
 All participants in the Safety Population and have evaluable plasma, urine, or tissue concentration data for gepotidacin. A subject is considered to have evaluable PK data for gepotidacin if the subject has at least 1 measurable post-dose PK concentration value for gepotidacin that was not excluded from the analysis due to a protocol deviation. This primary analysis population will be used in the assessment and characterization of PK concentrations (summary tables, listings, and figures) 	
 PK Concentration
PK Parameter	
 All participants in the PK Population who receive gepotidacin 1500 mg BID through the completion of all PK collections for whom valid and evaluable plasma or urine PK parameters are derived for gepotidacin. This primary analysis population will be used in the assessment and characterization of PK parameters (summary and analysis tables, listings, and figures) 	
 PK Parameter
Intent-To-Treat (ITT)	
 All participants that met all eligibilities and were assigned to study treatment 	
 Study Population
Microbiological ITT (micro-ITT)	
 All participants in the ITT Population, receive at least 1 dose of gepotidacin, and have a qualifying baseline uropathogen from a quantitative bacteriological culture of a pretreatment clean catch midstream urine specimen. The algorithm of the qualifying bacterial uropathogen is presented in Appendix 4: Derived and Transformed Data, Figure 2. 	
 Efficacy
PKPD	
 All participants in both the PK Parameter Population and the Micro-ITT Population 	
 PKPD

Refer to [Appendix 9: List of Data Displays](#).

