9.1.1.1. Microbiological Outcome and Response

- The microbiological outcome and response to study treatment will be determined by prespecified programmed algorithm for each participant/qualifying uropathogen.
- The microbiological outcome is determined by comparing the baseline culture results to the culture results at each subsequent visit. The corresponding microbiological response “by qualifying uropathogen” is then assigned. The criteria of microbiological outcome and response are shown in [Table 4](#), [Table 5](#), and [Table 6](#).
- Participant level microbiological success refers to participants who have been deemed a “microbiological success” for all their “qualifying baseline uropathogen” microbiological responses.
- All other combinations are deemed failures for participant level microbiological response.
- Participants who withdraw from the study prior to TOC or Follow-Up Visits will be considered not achieving success as the microbiological response. Microbiological outcome will be derived and listed at early termination visit.
- Microbiological outcome and response along with the 95% Clopper-Pearson CI for the percentage of microbiological response will be summarized for qualifying uropathogens isolated at baseline using the groups listed below at the On-therapy, TOC, and Follow-up visits using counts and percentages. Participant level microbiological response and 95% Clopper-Pearson CI will be summarized within the same table. The necessity of these categories will depend on the uropathogens that are recovered. Any additional uropathogens present in 10 or more participants will be

summarized separately. Additional uropathogens present in less than 10 participants will be grouped into the combined categories (eg, other beta-hemolytic streptococci).

- *Escherichia coli*
 - Quinolone-resistant *E. coli*
 - Extended spectrum beta-lactamase (ESBL) producing *E. coli*
 - Multidrug-resistant (MDR) *E. coli*
- Other gram-negative bacilli
- *Staphylococcus aureus*
- *Staphylococcus saprophyticus*
- Coagulase-negative staphylococci
- Beta-hemolytic streptococci
- Viridans streptococci
- *Enterococcus* spp.
- *Gardnerella vaginalis*
- *Aerococcus urinae*
- Other Gram-positive uropathogens
- A participant will be counted multiple times under an uropathogen category if multiple qualifying uropathogens within that uropathogen category are isolated at baseline for the participant.

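### Qualifying-uropathogen status is flagged from an isolate list that shows participant, visit and postbaseline cultures, with no masking or lock date (minor)

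*SAP*

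**What the plan says.** SAP 12.4.4 (Microbiological Data Procedures) describes an exchange. First, "Statistics and Programming will also provide a list of all distinct isolates (by participant, visit, identification, and quantitative bacterial count") to the microbiologist and clinical scientist. Visit is one of the keys, and nothing restricts the list to baseline. They then return a spreadsheet of organism codes with "a flag to indicate which items within the code list are uropathogens and qualifying uropathogens for this protocol", and that flag is merged into SDTM. Earlier in the same section (Microbiology Procedures), what they supply is described differently, as "clarification of which isolates should be labelled as uropathogens and qualifying uropathogens".

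The flag is used in several places:

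- **Micro-ITT.** SAP Section 4 requires that participants "have a qualifying baseline uropathogen from a quantitative bacteriological culture of a pretreatment clean catch midstream urine specimen". SAP 12.4.2 adds: "The algorithm of the qualifying bacterial uropathogen is presented in Figure 2". It also sets a baseline count rule of at least 10^5 CFU/mL for one of the organisms when two uropathogens are found.
- **Default efficacy and PKPD populations.** SAP 9.1.3 bases efficacy on micro-ITT unless otherwise specified. Section 4 defines the PKPD population as the overlap of micro-ITT and the PK Parameter population.
- **Displays.** The programming notes for Tables 2.3 and 2.4 (SAP 12.9.5) identify qualifying uropathogens as those flagged by these two people.
- **New organisms.** In SAP Tables 4 to 6, an organism not present at baseline counts as superinfection, new infection or colonization only if it is qualifying.

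The outcome itself "will be determined by prespecified programmed algorithm for each participant/qualifying uropathogen" (SAP 9.1.1.1). On blinding, Protocol 7.4 says: "This will be an open-label study".

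**The concern.** A rule for who enters an efficacy denominator should be fixed without sight of the outcome. Here a human classification feeds the denominator, and those who make it hold each participant's postbaseline isolates and counts. If a less common organism grew again after treatment, they can see that while deciding whether it counts. Leaving it out would remove a microbiological failure.

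No date protects the step. SAP 3.1 ties the final analysis to database freeze but sets no earlier lock for the organism list. SAP 12.9.3 plans a dry run during the study, and the efficacy tables are marked for that delivery as well as the final one.

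At stake are the micro-ITT success rates and their Clopper-Pearson intervals, the PKPD summaries, and the labels given to new organisms. The interval describes sampling error only; it does not reflect uncertainty about who belongs in the denominator. No misuse is alleged. The point is that the plan leaves a route open that it does not need.

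**Working it through.** The plan gives no figure to reproduce. The check is a reading of the text, followed by an illustration of size.

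**1. What the flaggers can see.** The fields are participant, visit, identification and count. An organism present at baseline and again at a later visit is therefore visible as persistence or recurrence. Success is not visible. A missing later isolate may mean eradication or an uncollected sample, and the latter is undetermined (SAP 12.4.4) and a failure at Test-of-Cure (SAP Table 5). Symptom scores and other antibacterial use, which also decide response, are not among the listed fields.

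**2. What they can change.** The returned flag is on items of a code list, so one call covers every participant with that organism. Membership also needs a pretreatment culture and the baseline algorithm, neither of which depends on later cultures. A participant leaves micro-ITT only if the organism was her sole qualifying one. The room for choice is therefore the set of less common species. The other sentence, which speaks of isolates, could be read as allowing a choice isolate by isolate.

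**3. How many participants a species call may cover.** Protocol 5.2 enrols 25 to 30. Protocol 3.2 expects 75% to 90% *E. coli* and 5% to 15% *S. saprophyticus*, with *Klebsiella*, *Enterobacter*, *Proteus* and enterococci together in 5% to 10%. Assuming every enrolled participant grows a pathogen, that last group is 25 × 0.05 = 1.25 to 30 × 0.10 = 3.0 participants in total. A single less common species may therefore occur in only one or two.

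**4. Size.** Micro-ITT size and success rate are assumptions: n from 8 to 25, with 80% success (75% at n = 8). With x successes among n, removing f failing participants moves the rate from x/n to x/(n − f), a shift of x·f/[n(n − f)]. The exact 95% limits for x of m are the 0.025 quantile of Beta(x, m − x + 1) and the 0.975 quantile of Beta(x + 1, m − x); when x = m the upper limit is 100%.

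| n | As classified | One failure removed | Shift (points) | Two failures removed | Shift (points) |
|---|---|---|---|---|---|
| 8 | 6/8 = 75.0% (34.9 to 96.8) | 6/7 = 85.7% (42.1 to 99.6) | 10.7 | 6/6 = 100% (54.1 to 100) | 25.0 |
| 10 | 8/10 = 80.0% (44.4 to 97.5) | 8/9 = 88.9% (51.8 to 99.7) | 8.9 | 8/8 = 100% (63.1 to 100) | 20.0 |
| 15 | 12/15 = 80.0% (51.9 to 95.7) | 12/14 = 85.7% (57.2 to 98.2) | 5.7 | 12/13 = 92.3% (64.0 to 99.8) | 12.3 |
| 20 | 16/20 = 80.0% (56.3 to 94.3) | 16/19 = 84.2% (60.4 to 96.6) | 4.2 | 16/18 = 88.9% (65.3 to 98.6) | 8.9 |
| 25 | 20/25 = 80.0% (59.3 to 93.2) | 20/24 = 83.3% (62.6 to 95.3) | 3.3 | 20/23 = 87.0% (66.4 to 97.2) | 7.0 |

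**5. Effect of a code-level call.** Because the call takes successes with it, the shift shrinks as the species becomes more common. From 8/10, dropping a species with one failure and one success gives 7/8 = 87.5%. Dropping one with one failure and four successes gives 4/5 = 80.0%, no change. Only rare species matter.

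**The case against.** The strongest case against is that little is left to choose. The flag is on organism codes, membership rests on the pretreatment culture and count, and the algorithm figure may already name the organisms. That figure is not shown in the copy reviewed, and its absence there is no fault of the plan. Efficacy is exploratory (Protocol 9.1), no hypothesis is tested (SAP 2.4), there is no comparator, and no decision rule hangs on the success rate. All of this stands, and it limits the point to a minor one. It does not remove the point: the text still assigns the flag to people holding the keyed list and sets no date.

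A reader might infer more than the documents support:

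- *That this step alone fixes micro-ITT, participant by participant.* The code-level wording and the baseline algorithm say otherwise. Only the looser sentence about isolates leaves that reading open.
- *That a selective exclusion could not be detected.* Listing 3 shows participants excluded from any population, Listing 14 gives ITT culture results, and Listing 16 pages participants in and out of micro-ITT. The exclusion would be visible, though not the reason behind it.
- *That this is the only discretionary step in the efficacy derivation.* The investigator's clinical outcome (SAP 9.1.1.3) and the microbiologist's strain matching (SAP 12.4.4) also involve judgement.
- *That the flaggers can tell whether a call adds a success.* They see regrowth, not full response.
- *That the coagulase-negative staphylococci, viridans streptococci or* Gardnerella *in SAP 9.1.1.1 are open calls.* They appear there as display groups, so this cannot be established without the figure.

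It is also fair to say that some keyed review is necessary. For participants with two retained strains, "Statistics and Programming will provide all central laboratory data from all visits for the particular uropathogens to the microbiologist", and that matching across visits cannot be done without participant and visit.

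**Conclusion.** The point holds as a minor one. As written, the SAP lets the qualifying-uropathogen flag be set with postbaseline persistence or recurrence in view, without masking, baseline-only restriction or a lock date. The exposure is the classification of less common species, and it falls away to the extent that the algorithm figure already names the organisms and is stated to govern.

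Under assumed micro-ITT sizes of 8 to 25 and about 80% success, one failing participant removed moves the success rate by about 3 to 11 points, and two by about 7 to 25. The upper ends need a small micro-ITT and a species confined to failures. The PKPD population and the superinfection, new infection and colonization categories also use the flag; the primary PK analysis does not.

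**What to change.** Amend SAP 12.4.4 and the transfer specification as follows:

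1. Send the microbiologist and clinical scientist a list of unique organism names, with count category if they need it, and no participant or visit.
2. Have the code list signed and frozen before any postbaseline culture is released to them. If the algorithm figure already names the organisms, say that it governs.
3. Classify organisms first seen later from the same kind of list without keys.
4. Derive micro-ITT by program from the frozen list and the Figure 2 baseline algorithm.
5. Reconcile the two descriptions in 12.4.4 by stating that the flag is at organism-code level.
6. Keep participant- and visit-keyed data only for same-visit duplicates and cross-visit strain matching.

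The cost is one revised transfer specification and a sentence or two in the SAP. No extra data, staff or samples are needed.
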